## II. Specific Aims

We propose a randomized clinical trial with **primary aims** to evaluate the: **1)** use, **2)** consequences (on cessation), and **3)** mechanisms of varenicline sampling. We will recruit between 648-660 smokers and randomize them to receive a 4-week sample of varenicline, NRT, or no sample, and will follow all for 6 months. Our remote focus derives from our hands-off (i.e., translatable) intent, yet our methods include both daily diary assessment and remote biological verification of smoking to enhance rigor. We are mindful of requirements for physician oversight and embed full precautions for safety. Our study sample will include smokers both wanting to quit and not (recruitment of each, with stratified randomization), which will allow for exploratory sensitivity analyses to assess the role of smoker motivation on outcomes.

In accordance with these Aims, we hypothesize that: 1) use of varenicline will be strong: >80% of study sample using medications on at least 50% of the sampling period; 2) relative to non-medication controls, sampling will result in higher incidence of quit attempts and biochemically verified cessation; 3) with greater changes in hypothesized mediators (motivation/confidence, decreases in treatment fatigue). Comparisons of varenicline vs NRT sampling a) uptake, b) mechanisms and c) outcomes are secondary but nonetheless compelling and offer additional significance, innovation, and rigor to our trial.

[figure not shown]

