**Figure of Study Flow for STARS**

Randomization, Stratification We recruit smokers wanting to quit ( $\geq 7$  on 0-10 scale) and not, and we use this as a stratification variable. We considered a number of other stratification variables (e.g. cigs/day, insurance status) but believe that randomization will adequately handle these. We will randomize participants to group in a 2:1:1 ratio, with intent to increase precision of our parameter estimates within the varenicline group (n=324), consistent with our intent to understand use patterns and uptake of varenicline.

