### *III f Assessments*

All interview data are entered in real time within a REDCap database, ensuring high data quality. We have established assessment protocols for all outcomes. Our follow-up interview has been extensively used in our prior studies and is timed at ~20 minutes. Self-report data include the following:

Baseline questionnaire will ascertain basic demographics and smoking history, including measures of dependence,(88) prior use of medications, and all hypothesized mediators (\*listed below).

Smoking (Reduction) Using Timeline Follow Back (TLFB) methods, we assess cigarettes per day over the previous seven days, and from this can calculate abstinence (defined below), as well as smoking reduction, and percent who achieve 50% reduction. We also track use of other tobacco products, including e-cigarettes.

Abstinence is defined as both “floating” (any 7 day period of non-smoking) and point prevalence, as recommended for “cessation-induction” studies.(89) We will track longest duration of abstinence and relapse following stated quit attempts.

Quit Attempts We will track the incidence of any self-defined and “serious” quit attempts over the 3-month follow-up period. The latter is the typical measure of quit attempts, used in CDC reports, and is defined as an attempt lasting  $\geq 24$ hrs. We will also report on the maximum duration, and latency of each QA since baseline.

Use of varenicline, NRT other meds We will determine the incidence and frequency of medications used, both during the sampling period and beyond. For varenicline, we will assess actual dosage used as well as titration patterns, days of use, and whether or not the person “converted” to sustained use (when, how, through whom).

\*Self-Efficacy, Motivation, & Confidence to Quit We will use single item (0-10 visual analog scale) measures for each. Our ladders have adequate test-retest stability and predictive validity.(90)

\*Attitudes Towards varenicline, NRT Based largely on prior work in this area(58, 91), we have published(25, 75) on 1) positive, and 2) negative attitudes towards medications, as well as 3) general knowledge of them.

\*Treatment Self-Regulation Questionnaire The TSRQ(47) is a well-established measure of autonomous motivation; i.e., the degree to which decisions on quitting are self-determined and/or controlled by others.

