### *III g Electronic Diaries during Sampling*

All participants will be asked to complete a brief diary to assess smoking behavior and use of meds. These diaries, which will include brief mood assessments, provide additional, real-time risk monitoring, not to replace traditional adverse event assessment (above), but to complement. Our intent is to better capture day-to-day fluctuations in medication use and smoking. Each of our recent trials have used this diary approach, with excellent compliance (88% for one study, 83% for another). Diaries will assess cigarettes smoked per day, medications/products used, purposes of that use (to reduce/quit), and mood/affect. Diaries ( $\leq 2$  min each) will be electronically collected daily throughout the sampling period (28 days). We have established procedures to auto-send an email/text on a set schedule. Thus, per eligibility criteria above, we require participants to have smartphone capacity, and they will be compensated for compliance based on % diaries completed (e.g., \$100 for 90-100% compliance, \$70 for 75-90% compliance, etc.). There is some debate as to whether EMA/diary procedures alter behavior, but recent evidence suggests not,(95, 96) but even if so this is equal between groups.

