Mechanisms of Change: We hypothesize that varenicline sampling will enhance quit motivation & confidence, as well knowledge of and attitudes toward medication, autonomy to quit, and will decrease cessation fatigue. We will examine all through analyses of continuous outcomes above. It will be interesting to explore whether and how these non-pharmacologic mechanisms differ for varenicline vs. NRT. Medication expectancies, knowledge, and familiarization might differentially vary through varenicline/NRT sampling, as might motivation and confidence. Note that our focus is on non-pharmacologic mechanisms, since the pharmacologic mechanisms of both varenicline and NRT are well-established and also since our design does not include a placebo comparator. Also note that formal tests of mediation can be explored but we may not be powered for these.

Diary Analyses: Mixed effects regression models(101) will be used to model diary data outcomes (e.g., days of med use) to allow for repeated observations per participant as well as for time-invariant (group, gender, etc.) and time-varying covariates (e.g., motivation to quit). These types of models allow for the inclusion of incomplete data across time, so we can include all reported data, even if <28 days per ppt. Any results obtained from these mixed effects models will be considered exploratory and primarily used to gather information on effect sizes.

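### Diary models: time-varying motivation to quit is a hypothesised mediator, so a model that includes it does not estimate the total effect of sampling

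*Combined protocol and SAP*

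**What the plan says.** Section IIIi, Diary Analyses, plans mixed effects regression for diary outcomes, with days of medication use as the example. Group and gender are examples of time-invariant terms; the time-varying terms are described as "time-varying covariates (e.g., motivation to quit". On status, the paragraph says: "Any results obtained from these mixed effects models will be considered exploratory and primarily used to gather information on effect sizes".

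The plan gives motivation a second role. The Aim 3 hypothesis in section II expects sampling to work "with greater changes in hypothesized mediators (motivation/confidence, decreases in treatment fatigue". The Mechanisms of Change paragraph, just before Diary Analyses, states: "We hypothesize that varenicline sampling will enhance quit motivation & confidence". Section III f (Assessments) stars motivation as a mediator and specifies its measurement: "We will use single item (0-10 visual analog scale) measures for each".

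Section III g lists the diary content: "Diaries will assess cigarettes smoked per day, medications/products used, purposes of that use (to reduce/quit), and mood/affect". Diaries are "electronically collected daily throughout the sampling period (28 days". No motivation item is listed. Wanting to quit, scored 7 or more on a 0-10 scale, is also used at randomisation: "we use this as a stratification variable".

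**The concern.** Randomisation protects the comparison of groups as assigned. It does not protect a comparison made at equal values of something that assignment has since changed. If sampling raises motivation and motivation in turn affects smoking or medication use, holding post-randomisation motivation fixed takes out the part of the effect that runs through it. It also opens a path through any unmeasured cause shared by motivation and the outcome. What remains is a direct-type effect that holds only under assumptions the plan does not state.

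The diary models are meant to supply effect sizes, and nothing in the plan says whether the group coefficient is a total or a conditional effect. A reader could take a conditional coefficient as the effect of being given a sample, when it is net of a mechanism that the trial itself proposes.

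There is also a gap in execution. A time-varying covariate needs values over time, and the diaries as listed do not supply them.

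**Working it through.** The plan gives no figure for the diary analyses, so there is none to reproduce. The check is textual, followed by an illustration of size.

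**1. Role of motivation.** Diary Analyses allows group and time-varying motivation in the same model. Section II, section III f and Mechanisms of Change all treat motivation as something sampling is expected to change. Elsewhere in section IIIi, covariates for binary and continuous outcomes are limited to baseline differences, so the diary models are the only place where a post-randomisation covariate is offered.

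**2. Available values.** Motivation is measured at baseline (section III f has all starred mediators in the baseline questionnaire) and is otherwise a questionnaire item. Follow-ups fall at +17 and +33 days, then at 2, 3 and 6 months. Within a 28-day diary window this gives about two values, baseline and +17 days; +33 days falls just after it. No rule links these values to diary days. Assigning a +17 or +33 value to an earlier day would condition on motivation measured after the outcome.

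**3. Path arithmetic.** Total effect = c + a × b, where c is the direct effect, a the effect of group on motivation, and b the effect of motivation on the diary outcome. Full adjustment for motivation removes a × b.
- a = 0.46 SD, from NRT Sampling Study 1 in Preliminary Studies (change of 2.0 against 0.4 points). It is borrowed here for varenicline against control.
- b is not in the documents. Assumed values are 0.1, 0.3 and 0.5 SD per SD.
- Removed: 0.46 × 0.1 = 0.046; 0.46 × 0.3 = 0.138; 0.46 × 0.5 = 0.230 SD.

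**4. Effect of sparse measurement.** A small simulation used 324 against 162 participants, 28 days, a random intercept, direct effect 0.20, an unmeasured common cause of motivation and outcome, and 8 replicates per setting. Motivation shifts from day 3, so the true total is 0.20 + b × 0.46 × 26/28. Carried forward means the baseline value to day 16 and the day-17 value thereafter. Group coefficients with a = 0.46:

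| b | True total | Unadjusted | Baseline motivation | Carried forward | Daily motivation |
|---|---|---|---|---|---|
| 0.1 | 0.243 | 0.258 | 0.261 | 0.248 | 0.202 |
| 0.3 | 0.328 | 0.292 | 0.279 | 0.262 | 0.141 |
| 0.5 | 0.414 | 0.368 | 0.355 | 0.334 | 0.154 |

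Simulation noise is about 0.02 to 0.04 per estimate. Columns in a row share the same simulated data, so differences from the unadjusted column are the more useful reading:
- Daily motivation: 0.258 − 0.202 = 0.056; 0.292 − 0.141 = 0.151; 0.368 − 0.154 = 0.214.
- Carried forward: 0.258 − 0.248 = 0.010; 0.292 − 0.262 = 0.030; 0.368 − 0.334 = 0.034.

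With a = 0, the unadjusted estimates were 0.191, 0.237 and 0.200, and the daily-adjusted ones 0.193, 0.217 and 0.211, against a true 0.20. There was no systematic shift.

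**The case against.** The strongest reply is that the plan does not commit to this adjustment. The sentence describes what mixed models can accommodate and offers motivation as an example. Effect sizes need not mean group effects; a within-person association between motivation and use is a common reason for a time-varying covariate. This stands: the documents show a model that is permitted, not one fixed for every diary outcome.

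Second, the diary outcome named is medication use, and section IIIi focuses usage outcomes within each active group. The comparison of varenicline with NRT is possible, but the plan leaves open whether motivation differs between them; if it does not, no systematic shift is expected. This stands too, and it limits the problem mainly to contrasts with control, such as diary cigarettes per day.

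Third, the results are exploratory, and the main group comparisons are made elsewhere by chi-square or Fisher tests and general linear models with covariates only for baseline differences. That is correct, and it limits the consequence. It does not make a conditional coefficient interpretable as a total effect.

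A reader might infer that the diary effect sizes will be biased by a known share, for example 0.046/0.3 = 15% to 0.138/0.3 = 46% of a 0.3 SD effect. The documents do not support that. Neither the 0.3 SD effect nor the slope is in them. The 0.46 comes from lozenge sampling against no sampling in smokers recruited as unmotivated, with both arms asked to try a practice quit attempt, whereas this trial also enrols smokers who want to quit. The calculation further assumes full daily adjustment, which the listed measurements cannot provide. Nor does the absence of motivation from the diaries cause bias in itself; it leaves the matching rule unspecified.

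**Conclusion.** The point holds conditionally. If post-randomisation motivation enters a diary model, the group coefficient is a conditional, direct-type effect open to motivation-outcome confounding. It misstates the total effect of sampling for any contrast in which sampling changes motivation, most plausibly sampling against control.

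The size is unknown from the documents. Under the borrowed a of 0.46 and assumed slopes of 0.1 to 0.5, full daily adjustment would remove about 0.05 to 0.23 SD. With baseline and +17-day values carried forward, the likely shift is small: about 0.01 to 0.03 SD in a simulation of only 8 replicates that assumes an early shift in motivation.

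The six-month abstinence comparison, the other main outcomes and the sample size are untouched. This is a matter of keeping exploratory effect sizes interpretable and the model executable. It is worth correcting because the correction is specific and needs no new data.

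**What to change.** Amend the Diary Analyses paragraph in three respects.

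1. Estimate diary group effects from models with group, time and baseline motivation (the randomisation stratum) as a time-invariant covariate, and no post-randomisation motivation. State that the group coefficient is the total effect of assignment.
2. Report any model with time-varying motivation separately, labelled as an exploratory mechanism or within-person association analysis. Do not present its group coefficient as the effect of sampling.
3. For that second model, state where the motivation values come from and how they are matched to diary days. Use only values measured on or before the diary day, so that neither the +17-day nor the +33-day value is assigned backwards.

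The cost is a few sentences of specification. Baseline motivation is already collected and already used for stratification, no assessment is added, and the time-varying analysis remains available under its own label.

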### *Conclusions*

In an era when most intensive treatments do not lend themselves to real-world implementation, medication sampling represents a brief, concrete, easy to explain strategy that has strong empirical and theoretical support. Sampling extends the reach of treatment, and thus offers both clinical and policy significance. The proposed varenicline sampling study is not merely a rote extension of our NRT sampling work. Yet like our prior work, we believe that varenicline sampling offers another and potentially stronger catalyst for further engagement in the quitting process. This R01 wholly conforms to recommendations for pragmatic trials,(102, 103) in that our intervention is: rigorous, rapid, transparent, user-friendly, feasible, important to practitioners, and eventually broadly applicable.(104, 105) This application is also wholly responsive to PAR 18-869, and, as a modular R01, offers a tight, streamlined clinical trial that directly tobacco control, which is cancer control. Varenicline sampling, applied to a broad spectrum of smokers, could be yet another strategy to get more smokers to make evidence-based quit attempts, sooner.

104. Glasgow RE. What does it mean to be pragmatic? Pragmatic methods, measures, and models to facilitate research translation. *Health Education and Behavior* 2013;40:257-65.

**Protocol Amendments:** 31 amendments in total, all listed below. Details provided for all amendments that are NOT any of the following: a) change in study personnel, b) change in study advertising, or c) change in study assessments. All amendments received expedited (i.e., not full board) review.

Amend. #	Name	Date
31	Amendment 31 for IRB Study #Pro00098479 – 
 
• Staff change
 
	5/28/2025
30	Amendment 30 for IRB Study #Pro00098479 – 
 
• Fixing protocol version date
 
	10/14/2024
29	Amendment 29 for IRB Study #Pro00098479 – 
 
• Increasing upper limit of study sample from 648 to 660
 
	09/13/2024
28	Amendment 28 for IRB Study #Pro00098479 – 
 
• Staff change
 
	5/31/2024
27	Amendment 27 for IRB Study #Pro00098479 – 
 
• Staff change
 
	04/22/2024
26	iCO window change 
 
• Informed Consent: Changing the breathalyzer sample submission window from 24 hours to 72 hours.
 
	03/12/2024
25	Amendment 25 for IRB Study #Pro00098479 
 
• advertising
 
	03/07/2024
24	Amendment 24 for IRB Study #Pro00098479 
 
• Staff change
 
	1/19/2024
23	Increase iCO payment 
 
• Payment to participant language has been updated to reflect increase in breathalyzer sample from \$5 per sample to \$20 per sample. Total amount of payment for participants who complete all aspects of the study increased from \$225 to \$300.
 
	12/20/2023
22	new ads ONLY (from Build Clinical) 
 
• New advertising
 
	11/14/2023
21	Personnel Add Only 
 
• Staff change
 
	09/15/2023
20	Personnel Add Only 
 
• Staff change
 
	06/12/2023
19	Radio Ad 
 
• Adding advertisement through radio ad commercials.
 
	03/28/2023
18	New advertisements & addition of referral recruitment 
 
• New advertising
 
	02/21/2023
17	New Advertisements Only 
 
• Adding additional advertisement photos, flyers, and language.
 
	09/30/2022
16	New ads, remove personnel & removal of 50/50 split based on motivation to quit 
 
• new advertisements
 
• We are removing the requirement to recruit equal numbers of "motivated" and "unmotivated" smokers. We will continue to recruit from both groups and continue to stratify on this variable but will no longer exclude participants based on this criteria.
 
• Staffing change
 
	07/25/2022
15	New advertisements only 
 
• Three new study flyers
 
	06/22/2022
14	Add 2nd generic varenicline option; personnel addition 
 
• Add new generic varenicline (PAR) to ICD
 
• New personnel
 
	06/03/2022
13	Personnel Add Only 
 
• Staff change
 
	05/23/2022
12	Personnel Add Only 
 
• Staff change
 
	03/04/2022

11	Change medical record language on ICD 
 
• Sending study invitations to potential participants through EHR.
 
	02/25/2022
10	Addition of one advertising image & personnel changes 
 
• Updated advertising
 
• Staffing change
 
	02/08/2022
9	Changes to VRN source and bus ads 
 
• Consent form has been adjusted to reflect the option of giving the FDA authorized generic version of varenicline called Apo-varenicline that is approved and available for use in Canada. Until Chantix becomes available again in the US, we will offer Apo-varenicline in the study.
 
 
We had previously adjusted the script for those in the varenicline group and created a letter to send out to currently enrolled participants who have received varenicline to inform them of a voluntary recall of varenicline at the warehouse level due to impurities found during quality control testing. We now have removed these changes and have made the changes above to the consent form. We will move forward with fda authorized apo-varenicline or chantix once it becomes available again without impurities.
	08/11/2021
8	Changing Requirements RE: Having a doctor 
 
• Removing the requirement for participants to have a doctor that can prescribe them medications.
 
• Adding a mailed handout to give to ppts with instructions on how to have a telehealth visit for a prescription.
 
	06/30/2021
7	Amendment 7 for IRB Study #Pro00098479 -- Epic Recruitment 
 
• Recruitment through EPIC (EHR)
 
• Staffing change
 
	06/23/2021
6	Amendment 6 for IRB Study #Pro00098479 (New Ad Wording) 
 
• Revisions to advertising
 
	05/17/2021
5	Amendment 5 for IRB Study #Pro00098479 (New Ads) 
 
• New Flyers for Study Recruitment
 
• Staff change
 
	05/10/2021
4	Amendment 4 for IRB Study #Pro00098479 (Corrections to consent form and changed screening questions) 
 
• Fixed typos in consent form, adjusted screening/eligibility question from "Have you seen a doctor in the past year?" to " Do you have access to a medical provider who could write a prescription for you if you needed it?"
 
	04/07/2021
3	Amendment 3 for IRB Study #Pro00098479 (Eligibility corrected and assessment changes) 
 
• Assessments have been reorganized based on the needs of the study at different time points.
 
 iCO collection survey added. Correcting eligibility to require email for all participants (instead of email OR smartphone)	02/18/2021
2	Amendment 2 for IRB Study #Pro00098479 
 
• Adding questions to the demographics form for physician review.
 
• Adding DOB to baseline questionnaires.
 
• Adjusting consent form to clarify payment cut offs.
 
• Staffing change
 
	01/22/2021
1	Amendment 1 for IRB Study #Pro00098479 
 
• Assessments adjusted for clarity
 
• PHQ cutoff for intervention adjusted - in protocol
 
• Consent form adjusted to allow us to use screening data in the study
 
	09/30/2020
